2.2. Secondary Objectives and Endpoints

The secondary objectives and endpoints are presented in Table 2-2. (For estimands, see [Appendix 3](#).)

Table 2-2 Secondary Objectives and Endpoints

Objective(s)	Endpoint Descriptions
Secondary	

 To assess the binding antibody responses of ARCT-021 compared to placebo for priming vaccination 	
Binding antibody (BAb) responses will be evaluated in all participants receiving at least 1 administration of study vaccine (ARCT-021 or placebo).
 
 GMC and GMC ratio at all time points GMFR and SC at all time points after baseline

2.3. Exploratory Objectives and Endpoints

The exploratory objectives and endpoints are presented in Table 2-3.

Table 2-3 Exploratory Objectives and Endpoints

Objective(s)	Endpoint Descriptions
Exploratory	

 To evaluate cell-mediated immune (CMI) responses in participants receiving ARCT-021 versus placebo for priming vaccination 	
CMI responses to SARS-CoV-2 spike antigen may be measured in a subset of participants (CMI subset):
 
 Cytokine-producing SARS CoV-2 Spike protein-specific T-cells 
 as measured by flow cytometry and intracellular cytokine (Tumor necrosis factor (TNF) α, Interleukin-2 (IL-2), Interferon-γ (IFN- γ), IL-4, and IL-13) staining assay at all time points

 To evaluate safety, reactogenicity, and immunogenicity responses in participants receiving ARCT-021, ARCT-154, ARCT-165 versus placebo as booster vaccination given 6 months after priming vaccination 	
Safety:
 
 Any unsolicited AE initiating within 28 days after booster dose of study vaccine administration, by severity and relationship to study vaccine (ARCT- 021, ARCT-154, ARCT-165, or placebo) Any MAAE, NOCD, AE leading to discontinuation/withdrawal or SAE through Early Termination Safety laboratory assessment prior to and 7 days after booster vaccine administration by toxicity grade 
Reactogenicity:
 
 Any solicited local or systemic AE initiating within 7 days after booster vaccine administration, by toxicity grade 
Immunogenicity:
 
 Binding and neutralizing antibody responses (GMFR, SC, GMC, GMT, NAbs/BAbs ratio) before and after booster administration CMI responses before and after booster administration (CMI subset)

 To evaluate the incidence of confirmed COVID-19 in participants vaccinated with ARCT-021, ARCT-154, ARCT-165 versus placebo 	
Confirmed COVID-19 will be assessed in all participants starting 7 days after first study vaccine (ARCT-021, ARCT-154, ARCT-165, or placebo) administration and will include:
 
 Confirmation of COVID-19 symptoms Confirmation of SARS-CoV-2 infection by reverse transcriptase-polymerase chain reaction (RT-PCR) Collection of COVID-19 diagnoses made outside of study-related procedures

 To evaluate the incidence of asymptomatic SARS-CoV-2 infection in participants vaccinated with ARCT-021, ARCT-154, ARCT-165 versus placebo 	
Asymptomatic SARS-CoV-2 will be assessed in all participants starting 7 days after first study vaccine and will include:
 
 Confirmation of SARS-CoV-2 infection by RT-PCR Confirmation of seroconversion of SARS-CoV-2 nucleocapsid (N) antibody at timepoints after Day 14

 To assess for vaccine-associated enhanced respiratory disease (VAERD) following vaccination with ARCT 021, ARCT 154, ARCT 165 versus placebo 	
Confirmed COVID-19 cases will be evaluated by an unblinded Data Safety Monitoring Board (DSMB) for frequency and severity in ARCT 021-, ARCT 154-, ARCT 165-, and placebo-vaccinated participants

 To assess the immune responses of ARCT-021, ARCT-154, ARCT-165 compared to placebo using other exploratory assays (eg, plaque reduction neutralizing titer [PRNT], or assays evaluating for responses to SARS-CoV-2 variants) 	
If additional assays and the corresponding blood samples are available, additional immune antibody responses may be evaluated in some or all participants receiving at least 1 administration of study vaccine (ARCT-021, ARCT-154, ARCT-165 or placebo).

3. Investigational Plan

3.1. Overall Study Design and Plan

The overall study design is described below. For the final analysis, data for all participants through early termination will be included.

This is a multiregional, multicenter, Phase 2, randomized, observer-blind study designed to evaluate the safety, reactogenicity, and immunogenicity of the study vaccine in younger and older adult participants. Enrolled participants will be randomly assigned to receive either study vaccine ARCT-021 or placebo (sterile saline) as the priming vaccination series and ARCT-021, ARCT-154, ARCT-165, or placebo as the booster administration.

Approximately 600 participants (300 each in younger [≥ 18 to < 56 years of age in United States or ≥ 21 to < 56 years of age in Singapore] and older [≥ 56 years of age] participants) will be enrolled. At Day 0, participants will be stratified by age and then randomly assigned to one of the 4 groups (3 ARCT-021:1 placebo) to receive 2-doses of study vaccine and/or placebo (see Table 3-1) separated by 28 days and, at Day 208, participants will be randomly assigned to active booster vaccine or placebo for a third (booster) dose of study vaccine given at 180 days after second study vaccination (Day 208). At a subset of clinical sites, all enrolled participants will also undergo blood sampling for evaluation of CMI responses. For further details relating to the booster assignments, please refer to the protocol.

Participants who complete study procedures through Day 98 will be offered the opportunity to determine if they are eligible for study re-enrollment to ensure dosing with ARCT-021.

After Day 98 and until Day 198, participants will be contacted to determine whether they are interested, if eligible, in re-enrolling in the study in order to receive active study vaccine. Only participants who are assigned to Study Group 4 (placebo) may re-enroll into the study.

Participants who received ARCT-021 of any dose (Study Groups 1, 2, 3) are asked to remain on the study schedule. Those participants who choose to re-enroll into the study complete early termination procedures and are assigned a new participant number when they re-enter the study. For this interim analysis, the data from re-enrolled participants is not included.

Vaccine doses for primary vaccination will be assigned as shown in Table 3-1.

Table 3-1 **Study Group Assignments**

Stratification Groups	Study Groups	Priming Vaccination 1 (Day 0)	Priming Vaccination 2 (Day 28)	Booster Vaccination (Day 208)		
		Randomized 1:1:1:1		Booster randomization ratio: ARCT-021 : ARCT-154 : ARCT-165 : Placebo 1:1:1:1		
Younger adults ^a AND Older adults ^b	1	ARCT-021 7.5 µg	Placebo	ARCT-021 5.0 µg ARCT-154 5.0 µg ARCT-165 5.0 µg Placebo		
		ARCT-021 5.0 µg	ARCT-021 5.0 µg			
		ARCT-021 7.5 µg	ARCT-021 7.5 µg			
	4	Placebo	Placebo	If not re-enrolled at Day 98-198^c: Booster Vaccination (Day 208) Booster randomization ratio: ARCT-021 : ARCT-154 : ARCT-165 1:1:1 (No Placebo)		
				ARCT-021 5.0 µg ARCT-154 5.0 µg ARCT-165 5.0 µg		
				If re-enrolled (Day 98-198) Vaccination 1 (Day 0) Groups 1, 2, and 3 (No Placebo) Randomized 1:1:1	Vaccination 2 (Day 28)	Booster Vaccination (Day 208) 1:1:1:1 (Includes placebo)
				ARCT-021 7.5 µg	Placebo	Placebo ARCT-021 5.0 µg ARCT-154 5.0 µg ARCT-165 5.0 µg
				ARCT-021 5.0 µg	ARCT-021 5.0 µg	
				ARCT-021 7.5 µg	ARCT-021 7.5 µg	

a Younger adults: 18 to <56 years of age in US and 21 to <56 years of age in Singapore

b Older adults: ≥ 56 years of age

c See [Section 3.1](#)

4. General Statistical Considerations

Data from participants excluded from an analysis will be included in the applicable data listings but not included in the calculation of summary statistics for that analysis set.

For categorical variables, frequencies, percentages, and 95% CIs (where applicable) will be presented. All percentages will be rounded to one decimal place. The number and percentage will be presented in the form XX (XX.X), where the percentage is displayed in parentheses.

Continuous variables will be summarized using descriptive statistics (i.e., number of participants, mean, median, SD, minimum, maximum, and 95% CIs [where applicable]). All mean and median values will be formatted to one more decimal place than the actual value. Standard deviation values will be formatted to two more decimal places than the actual value. Minimum and maximum will be formatted to the same decimal place as the actual value.

When count data are presented, the percentage will be suppressed when the count is zero in order to draw attention to the non-zero counts. The denominator for all percentages will be the number of participants in the given treatment group within the analysis set of interest and stratification level (if applicable) unless otherwise specified in a footnote.

All CIs will be 2-sided and performed using a 5% significance level. No multiplicity adjustment will be made for this study where multiple treatment groups and endpoints are being evaluated.

All analyses adjusting for age group (≥ 18 to <56 years; ≥ 56 years) will use the values derived from age reported in the interactive response technology (IRT) which was used for randomization stratification.

Early termination visits will be summarized separately for the priming vaccination period and the booster vaccination period, respectively.

Analysis will be presented by study phase and study treatment group where applicable as per [Table 4-1](#) below:

Table 4-1 **Study Phase and Study Treatment Groups**

Study Phase	Study Treatment Groups	Shell Presentation of Treatment Group
Priming Vaccination	ARCT-021 7.5 µg - Placebo	A
	ARCT-021 5.0 µg - ARCT-021 5.0 µg	B
	ARCT-021 7.5 µg - ARCT-021 7.5 µg	C
	Placebo	D
Booster Vaccination	ARCT Priming - ARCT-021 Booster	E1
	Placebo Priming - ARCT-021 Booster	E2
	ARCT Priming - ARCT-154 Booster	F1
	Placebo Priming - ARCT-154 Booster	F2
	ARCT Priming - ARCT-165 Booster	G1
	Placebo Priming - ARCT-165 Booster	G2
	ARCT Priming - Placebo/No Booster	H1
	Placebo Priming - No Booster	H2
Priming Vaccination (Re-enrolled Subjects Only)	ARCT-021 7.5 µg - Placebo	A
	ARCT-021 5.0 µg - ARCT-021 5.0 µg	B
	ARCT-021 7.5 µg - ARCT-021 7.5 µg	C

For some summary tables of booster vaccination period, active boosters will be pooled, and treatment groups will be presented like the following:

Booster Vaccination	ARCT-021 7.5 µg - Placebo - ARCT Booster	A1
	ARCT-021 7.5 µg - Placebo - Placebo Booster/ No Booster	A2
	ARCT-021 5.0 µg - ARCT-021 5.0 µg - ARCT Booster	B1
	ARCT-021 5.0 µg - ARCT-021 5.0 µg - Placebo Booster/No Booster	B2
	ARCT-021 7.5 µg - ARCT-021 7.5 µg - ARCT Booster	C1
	ARCT-021 7.5 µg - ARCT-021 7.5 µg - Placebo Booster/No Booster	C2
	Placebo - ARCT Booster	D1
	Placebo - No Booster	D2

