5.1. Participant Disposition

The number and percentage of participants in the following categories (analysis sets defined in [Section 4.4](#)) will be summarized based on the following (where applicable):

- Randomized Set
- Intent-to-Treat Set
- Modified Intent-to-Treat Set (mITT)
- Per-Protocol Set (PP)
- Cell Mediated Immunity Analysis Subsets (CMI)
 - mITT-CMI
 - PP-CMI
- Safety Set

- Reactogenicity Set (Dose 1)
- Reactogenicity Set (Dose 2)
- Booster Randomized Set
- Booster Safety Set
- Booster Reactogenicity Set
- Booster Intent-to-Treat Set (Booster ITT)
- Booster Modified Intent-to-Treat Set (Booster mITT)
- Booster Per-Protocol Set (PP)
- Booster Cell Mediated Immunity Subset (Booster CMI)
 - Booster mITT-CMI
 - Booster PP-CMI

The number of participants in the following categories will be summarized based on participants screened:

- Number of participants screened
- Number and percentage of screen failure participants and the reason for screen failure

The number and percentage of participants in each of the following disposition categories will be summarized based on the Randomized set for the priming vaccination period:

- Received each dose of study vaccine for priming vaccination dose 1 and dose 2
- Prematurely discontinued before receiving the second dose of study vaccine and the reason for discontinuation
- Prematurely discontinued before receiving the booster dose of study vaccine and the reason for discontinuation
- Completed study
- Prematurely discontinued the study and the reason for discontinuation

A participant disposition listing will be provided, including informed consent, participants who completed the study injection schedule, participants who completed study, participants who discontinued from study vaccine or who discontinued from participation in the study, with reasons for discontinuation. Randomization data will be also provided in a listing.

A table summarizing the frequencies and percentages for the following will be provided by the primary vaccination treatment groups for Safety Analysis set:

- Participants who have completed booster vaccination and who are followed for 56 days post booster vaccination or less
- Participants who have completed booster vaccination and who have been followed longer (> 56 days but < 180 days after booster dose)
- Participants who have completed primary vaccination and who have been followed < 12 months

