8.2. Analysis of Immunogenicity Primary and Secondary Endpoints

8.2.1. Analysis of primary and secondary immunogenicity endpoints

Total NAbS and BAbS titers will be summarized using descriptive statistics (number of subjects (n), median, minimum and maximum) by each time point in priming vaccination period (Baseline, Days 14, 28, 42, 56, 208) and booster vaccination period (Day 208, 236, Early Termination). Summaries of priming vaccination and booster vaccination periods based on their corresponding mITT and PP analysis sets will be presented separately using the applicable treatment groups (Table 4-1). For the analysis of booster mITT analysis set, summary tables with active boosters pooled (as presented in Table 4-1; e.g., A1, A2, B1, B2, etc.) will also be presented.

The following statistics will be provided in the summary tables and/or figures:

- Geometric mean titer (GMT) with corresponding 95% CI will be provided at each time point. The 95% CIs will be calculated based on the t-distribution of the log-transformed values then back transformed to the original scale for presentation. GMT level and corresponding 95% CI will be plotted at each timepoint in priming vaccination period for mITT analysis set. Plots of the reverse cumulative distribution curves also will be provided by treatment group and visit in priming vaccination period for mITT analysis set.
- Geometric mean fold rise (GMFR) with corresponding 95% CI will be provided at each post-baseline timepoint over baseline. The 95% CIs will be calculated based on the t-distribution of the log-transformed values then back transformed to the original scale for

presentation. GMFR and corresponding 95% CI will be plotted at each timepoint in priming vaccination period for mITT analysis set.

- The number and percentage of subjects with fold-rise ≥ 2 and fold-rise ≥ 4 from baseline (Seroconversion) at each post baseline time points will be tabulated with the 2-sided 95% CI using the Clopper Pearson method at each post-baseline timepoint.
- Seropositivity at a participant level is defined as any detectable antibody level above the lower limit of quantification (LLOQ) for the specific assay and antibody measured at timepoints after baseline. Seropositivity rates will be provided with 2-sided 95% CI using the Clopper-Pearson method at each post-baseline time point.

The definition of seroconversion/seropositivity may depend on assay-specific performance characteristics. The conventions are as follows:

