8.3.2. CMI Analysis

CMI responses will be evaluated for CMI subset using parametric flow cytometry for quantification and phenotyping and cytokine staining for TNF- α , IL-2, IFN- γ , IL-4, and IL-13. Blood sampling will be performed at Days 0, 14, 28, 42, 56, 208, 215, 236, and Early Termination in participants enrolled at centers identified with capabilities for isolation of peripheral blood mononuclear cells (PBMCs). CMI testing will not be performed on participants re-enrolling at Day 98-198 (i.e., placebo participants who re-enter the study to receive ARCT-021 priming vaccinations).

Descriptive statistics (N, mean, SD, min, Q1, median, Q3, max) will be provided for each visit including change from baseline at each timepoint, where CMI results are available for the priming vaccination period (mITT and PP analysis CMI subsets) and booster vaccination period (Booster mITT CMI subset). When summarizing the Early Termination visit, only include observations within the booster vaccination period post day 236. The following CMI responses will be summarized:

- CD4+ T-cell responses background subtracted (combined pools): IFN- γ , TNF- α , IL-2, IFN- γ + TNF- α +, IFN- γ + TNF- α + IL-2+
- CD8+ T-cell responses background subtracted (combined pools): IFN- γ , TNF- α , IL-2, IFN- γ + TNF- α +, IFN- γ + TNF- α + IL-2+

- Th1/Th2 CD4+ T-cell responses background subtracted (combined pools): IFN- γ , IL-4, IL-4+ IL-13+, IFN- γ + / IL4+ IL13+

Box plots will be provided for the following for priming vaccination period (mITT CMI subset): CD4+/CD8+ IFN γ , IL4+IL13+, IFN γ +/IL4+IL13+, Th1/Th2.

Analyses will be performed overall and by age group (younger adults (≥ 18 - < 56 years), older adults (≥ 56 years)) for priming vaccination period (mITT CMI subset).

Summary tables and figures will exclude any data points collected at or after the first occurrence of the following intercurrent events: death, missed second ARCT-021 (if applicable) dose, use of immune-modifying drugs, and study infection. Summary tables and figures will exclude all data from subjects with early (before Day 7), active or prior SARS-CoV-2 infection at first vaccination.

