Estimand 2	
The GMT of total NAbs (primary) and GMC of BAbs (secondary) titers against SARS-CoV-2 from Day 14 up to Early Termination after initial priming vaccination with ARCT-021 and booster vaccinations (ARCT-021, ARCT-154, and ARCT-165) (exploratory) of each dose in healthy adults. Interest will lie in comparing the GMC of each dosing regimen to placebo (GMR).
 
The hypothetical strategy is used to estimate antibody levels had both scheduled vaccinations been received, and without any influence from immune-modifying drugs or non-study vaccines, or subsequent SARS-CoV-2 infection.
	mITT	
Values below the limit of quantification (LOQ) or limit of detection (LOD) will be replaced by LOQ/2 and LOD/2, respectively.
	
Total NAbs and BAbs levels will be summarized with descriptive statistics, including boxplots (on log scale versus time) by time point: Days 14, 28, 42, 56, 208, 236, Early Termination. GMTs with corresponding 95% CI will be provided at each time point. The 95% CIs will be calculated based on the t-distribution of the log-transformed values then back transformed to the original scale. GMFRs with corresponding 95% CI will be provided at each post-baseline timepoint over baseline. The 95% CIs will be calculated based on the t-distribution of the log-transformed values then back transformed to the original scale.
	
Supportive: For the priming vaccination period ANCOVA will be fitted to the natural log transformed antibody titers and antibody concentrations measured against SARS-CoV-2 with terms for treatment group, age group and natural log baseline titer by each post-vaccination immunogenicity visit. The geometric least squares mean (GLSM) and corresponding 2-sided 95% CI for each treatment group will be provided by visit. Geometric mean ratio (GMR), estimated by the ratio of GLSM, and the corresponding 95% CI will be provided to assess the difference between ARCT-021 vs. placebo groups at each visit.
 
Descriptive statistics, GMT/GMFRs based on t-distribution will be presented by the following analysis subgroups: age group, gender and country. ANCOVA models will be presented by gender and country.

Table 13-6 **Summary of Statistical Methods and Supportive Analyses**

Estimand Label	Estimand Description	Analysis Set	Main Estimation		Supportive Analysis
			Imputation/ Data/ Censoring Rules	Analysis Model/Method	

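### In the booster period, antibody results at Early Termination are summarized as one time point with no day window, although the visit can fall from weeks to several months after the booster.

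*SAP*

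**What the plan says.** SAP 8.2.1 summarizes neutralizing and binding antibodies "by each time point in priming vaccination period (Baseline, Days 14, 28, 42, 56, 208) and booster vaccination period (Day 208, 236, Early Termination"). GMT, GMFR, seroconversion and seropositivity are produced at each listed point. No window, minimum time or adjustment for time since booster is attached to Early Termination. Estimands 2 and 3 (SAP Appendix 3, Table 13-5) name it as their last time point, after the booster.

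Protocol Version 6.0 (synopsis) triggers the visit by participant withdrawal or by the sponsor's decision to end the study. The last booster date is 15 December 2021. The target date for the visit is 16 February 2022, extendable by up to two weeks.

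Elsewhere the SAP does recognize that this visit has no fixed timing:
- SAP 5.1 (disposition) separates "Participants who have completed booster vaccination and who are followed for 56 days post booster vaccination or less" from "Participants who have completed booster vaccination and who have been followed longer (> 56 days but < 180 days after booster dose").
- SAP 8.3.2 (cell-mediated responses) says that the Early Termination summary should "only include observations within the booster vaccination period post day 236".

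SAP 4.4.12 places participants who were not randomized to a booster but have booster-period antibody data in the placebo booster group. Table 4-1 labels the resulting column for ARCT-primed participants as placebo or no booster.

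The SAP is not consistent for the priming period. Section 4 says "Early termination visits will be summarized separately for the priming vaccination period and the booster vaccination period, respectively", and Table 13-6 (SAP 13.6) lists "Days 14, 28, 42, 56, 208, 236, Early Termination" without naming a period. SAP 8.2.1 and the estimand endpoints give Early Termination only after the booster.

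**The concern.** A GMT or seroconversion rate is normally read as the response at a known time after a dose. The booster-period Early Termination row cannot be read that way. It can combine a participant who withdrew a week or two after the booster, when titers may still be rising, with one sampled several months later, when they are probably falling. The resulting average depends on who left when and on how booster dates fell relative to a calendar cut-off.

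The placebo column has a further problem. Randomized placebo recipients and participants who never entered the booster randomization are different populations, and the protocol allows them different lengths of follow-up.

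What is at stake is the last reported value of Estimands 2 and 3. A reader could take it for a fixed-time post-booster level, and the tables as specified would not reveal the spread in timing.

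**Working it through.** **Inputs**
- Last booster 15 December 2021; target visit date 16 February 2022; extension up to two weeks (protocol synopsis).
- Follow-up of at least 56 days after the last vaccination. Maximum participation is Day 353 if boosted and not re-enrolled, and Day 396 if neither boosted nor re-enrolled (protocol 3.1).
- Nominal booster day 208, with a visit window of +60 days (Schedule of Events, booster table).
- Follow-up categories of 56 days or less, and more than 56 but under 180 days (SAP 5.1).
- Antibody half-life: not in the documents. 60, 80 and 100 days are assumed.

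**Step 1. Reproduce the plan's minimum.** From 15 December 2021 to 16 February 2022 is 16 + 31 + 16 = 63 days, or 63 + 14 = 77 with the extension. The stated minimum of 56 days reproduces.

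**Step 2. Range of time since booster.**
- Boosted on the last date, staying to termination: 63 days.
- Longest, boosted on nominal Day 208 and not re-enrolled: 353 − 208 = 145 days. A later booster shortens this.
- Withdrawals: no lower limit, since the visit occurs whenever the participant leaves.
- By the SAP's own categories: from 56 days or less up to under 180 days.

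**Step 3. What the range could mean for titers.** With exponential decline, the fold difference between times a and b is 2^((b − a)/h). For a = 63 and b = 145, b − a = 82:

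| Assumed half-life h | Exponent | Fold difference |
|---|---|---|
| 60 days | 82/60 = 1.37 | 2.6 |
| 80 days | 82/80 = 1.03 | 2.0 |
| 100 days | 82/100 = 0.82 | 1.8 |

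For scale, the plan's lower seroconversion threshold is a 2-fold rise.

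**Step 4. Antibody rule against cell-mediated rule.** Day 236 is 236 − 208 = 28 days after a nominal booster. Under SAP 8.3.2, earlier samples are left out of the cell-mediated Early Termination summary. Under SAP 8.2.1, they stay in the antibody summary for the Booster mITT set. The Booster per-protocol set (SAP 4.4.13) requires a valid Day 236 sample within 7 days either way, so it should lose most early withdrawals, but it keeps the later spread.

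A cut at Day 236 on the study-day scale is not enough by itself. SAP Section 1 counts study day from the first vaccination. A participant boosted at the end of the window, Day 208 + 60 = 268, who left on Day 275 would pass a Day 236 cut only 7 days after the booster.

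**Step 5. Placebo and no booster.** The participation limits are Day 353 and Day 396, a difference of 43 days. Without a booster, the visit can fall 396 − 208 = 188 days after nominal Day 208, against 145 for boosted participants, a group that includes placebo booster recipients if the limit is read as covering any booster dose.

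**Step 6. Priming period.** SAP Section 4 calls for a priming-period summary of the visit, Table 13-6 leaves the period open, and SAP 8.2.1 omits it from the priming list. These cannot all be followed as written. It matters because "Those participants who choose to re-enroll into the study complete early termination procedures" and only Study Group 4 may re-enroll (SAP 3.1). If priming-period antibody data were tabulated, the placebo column would include re-enrollment exits from the Day 98 to 198 offer period. The vaccine columns would contain only other exits, at any time.

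**The case against.** The strongest reply is that little depends on this row. Booster immunogenicity is an exploratory objective, the study tests no hypothesis, and the ANCOVA and Miettinen-Nurminen comparisons are confined to the priming period (SAP 8.2.2). Protocol 7.6.5 evaluates durability only up to Day 236, and SAP Section 1 already warns that interpretation beyond Day 56 may be limited. Booster assignment is randomized, so visit timing should balance in expectation across the randomized booster arms. All of this stands, and it limits the point to a reporting improvement. It does not tell a reader of the table what time the row represents.

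The fold differences can also be challenged. They compare two participants at the ends of the range, not the error in any planned GMT, and the half-lives are assumptions. That is correct. A reader might take the full 56 to 180 days and obtain 4.2-, 2.9- or 2.4-fold. However, 180 is the open upper bound of a disposition category, and the Day 353 limit implies at most about 145 days for boosted, non-re-enrolled participants.

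A reader might also infer that the priming antibody analysis mixes placebo re-enrollment exits with vaccine-arm withdrawals. The documents do not support that. SAP 8.2.1 does not list the visit among the priming antibody time points, the arms are separate columns, and no re-enrollment counts are given. What remains is the inconsistency in Step 6.

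On the placebo column, randomized placebo and unboosted ARCT-primed participants both had their last active dose in priming, and the column is openly labelled. The pooling is therefore visible, though the difference in follow-up is not.

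**Conclusion.** The point holds for the booster period, as a low-cost improvement. As written, SAP 8.2.1 pools antibody samples taken from soon after the booster to several months later into one Early Termination row. The SAP restricts the same visit for cell-mediated responses and already classifies follow-up by time since booster.

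For boosted, non-re-enrolled participants who stay to termination, the spread is about 63 to 145 days. That is a 2.6-, 2.0- or 1.8-fold titer difference between the extremes at assumed half-lives of 60, 80 or 100 days with exponential decline. Withdrawals extend the lower end. The effect on the reported GMT depends on the actual distribution of visit times, which the documents do not give.

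The documents do not support reading this as a flaw in a primary result, in the planned durability evaluation, or in the randomized comparison of booster vaccines. For the priming period, the finding is only that the SAP contradicts itself on whether Early Termination antibody data are summarized.

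**What to change.** In SAP 8.2.1:
1. Apply the cell-mediated rule to antibodies, counted from the actual booster date: include Early Termination samples only if taken 28 days or more after the booster. State the reference day for participants without a booster, and list the excluded samples.
2. Report the median and range of days since booster with each Early Termination row. Alternatives are bins finer than the existing 56-day cut, or listing the visit without summarizing it. The 56-day cut alone is too coarse, because 63 and 145 days fall in the same category.
3. Show randomized placebo separately from no booster at this visit.
4. Reconcile SAP Section 4 and Table 13-6 with SAP 8.2.1 on whether priming-period Early Termination antibody data are summarized. If they are kept, list them rather than compare arms, because only Study Group 4 can exit by re-enrollment.

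The cost is a few sentences in the SAP and a change of table layout, with no new data. The drawback is smaller numbers per row: the plan allows for booster groups of as few as 25 participants, so reporting median and range is likely to serve better than many bins.
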